9. PGI-C

The PGI-C is a 1-item tool assessing the change of HS start of taking the study medication by 5-point Likert-type scale. The tool is required for anchoring of other instruments and endpoints. [Appendix 10.10](#)

10. PGI-S

The PGI-S is a 1-item tool assessing the severity of HS over the last week by 4-point Likert-type Scale. The tool is required for anchoring of other instruments and endpoints. [Appendix 10.11](#)

5.1.1 Patient diary

The Patient Global Assessment of HS Pain will be completed on a daily diary by subjects from Screening through Week 12.

If pain diaries are not completed for at least the seven consecutive days just prior to the Baseline visit, the subject may not be randomized.

The Patient Global Assessment of HS Pain will be used to assess the worst HS pain. Ratings will range from 0 (no HS pain) to 10 (HS pain as bad as you can imagine).

For the daily assessments being completed from Screening to Week 12, subjects should be instructed to complete the assessment before they go to bed, and respond to the items based on a recall period of the "last 24 hours".

Further instructions on diary and diary completion can be found in the ISF.

5.2 ASSESSMENT OF SAFETY

Safety will be assessed descriptively based on:

- Physical examination
- Vital signs
- Clinical laboratory values (haematology, clinical chemistry, coagulation and urinalysis)
- 12-lead ECG
- Adverse events
- Serious adverse events (SAEs)
- Intensity of adverse events will be assessed by Rheumatology Common Toxicity Criteria (RCTC) version 2.0 (refer to ISF for details)

5.2.1 Physical examination

Physical examinations will be performed at the time points specified in the [Flowchart](#).

A complete physical examination will be done at screening. It includes at a minimum general appearance, neck, lungs, cardiovascular system, abdomen, extremities, and skin.

For subsequent visits, targeted physical examinations will be done. These will include the evaluation of organ systems associated with AE(s) symptoms or laboratory abnormalities.

Measurement of height and body weight and waist circumference will be performed at the time points specified in the [Flowchart](#). BMI will be automatically calculated.

The results must be included in the source documents available at the site.

5.2.2 Vital signs

Vital signs will be evaluated at the time points specified in the [Flowchart](#), prior to blood sampling.

This includes temperature, respiratory rate, systolic and diastolic blood pressure and pulse rate (electronically or by palpation count for 1 minute). Respiratory rate, pulse rate, and blood pressure will be measured after patients have been sitting comfortably for at least five minutes. The results must be included in the source documents available at the site. Measurement of vital signs should precede blood sampling to avoid the impact of blood sampling on the vital measurements.

Vital signs will be measured additionally 10 min post-dose after s.c. administration and 5 and 60 min. post-dose in case of i.v. study drug administration.

Hypersensitivity reactions should be treated according to medical standards. Pre-medications for further injections might be considered and will be agreed on between investigator and the Sponsor.

5.2.3 Safety laboratory parameters

Safety laboratory parameters to be assessed are listed in Table [5.2.3:1](#) and [5.2.3:2](#). For the sampling time points please see the [Flowchart](#). More frequent blood sampling may be done whenever the investigator deems necessary. Unscheduled safety laboratory examinations will be reported in the CRF along with the results.

All safety laboratory analyses will be performed by a local laboratory.

It is preferred but the patients do not have to be fasted for the blood sampling for the safety laboratory.

It is the responsibility of the investigator to evaluate the laboratory results from the local laboratory.

Clinically relevant abnormal findings as judged by the investigator will be reported as baseline conditions or adverse events (please refer to [section 5.2.6](#)).

A clinically relevant value may be either in- or outside the reference range. Clinically relevant abnormal laboratory test results must be confirmed and should be repeated until normalization or stabilization or until an alternative explanation has been found. Abnormal laboratory values will be also graded for intensity by using RCTC Version 2.0 criteria. [[R13-3515](#)].

In case the criteria for hepatic injury are fulfilled, a number of additional measures will be performed (please see [section 5.2.6.1](#)) and the DILI Checklist provided in the ISF eDC system. The amount of blood taken from the patient concerned will be increased due to this additional sampling.

Table 5.2.3:1 Infection testing at screening and EoT visit

Category	Test name
Infection Testing	Hepatitis B Surface Antigen (qualitative) ⁵ Hepatitis B core Antibody ⁵ HBV-DNA (quantitative) at screening and EoT Visit ¹ Hepatitis C Antibodies (qualitative) ⁵ HIV-1, and HIV-2 Antibody (qualitative) ⁵ QuantiFERON®-TB-Gold Plus ^{2, 3, 4} T-spot TB test
Serum Pregnancy test (only for female patients of childbearing potential)	Human Serum Chorionic Gonadotropin

1 A HBV-DNA should be conducted if Hepatitis B core Antibody is positive and Hepatitis B Surface Antigen is negative. These evaluations should be conducted at screening and at the EoT visit

2 There is the trial site option to perform a PPD skin test.

3 Patients with indeterminate QuantiFERON or invalid/borderline T-spot may be retested with IGRA (once) and if inconclusive should have a PPD skin test. .

4 In subjects with a negative QuantiFERON®-TB-Gold Plus or PPD skin test, the test should be repeated at the EoT visit. Results of the PPD test should be collected in the CRF.

5 If determined as negative at screening, there's no need to retest at EoT.

Table 5.2.3:2 Safety laboratory tests

Category	Test name
Haematology	Hematocrit (Hct) Hemoglobin (Hb) Glycosylated Hbc (HbA1c) (Only at baseline) Red Blood Cell Count/ Erythrocytes Reticulocyte Count White Blood Cells / Leukocytes Platelet Count/ Thrombocytes
Diff. Automatic	Neutrophils (relative and absolute count) Eosinophils (relative and absolute count) Basophils (relative and absolute count) Monocytes (relative and absolute count) Lymphocytes (relative and absolute count)
Diff. Manual (if Diff Automatic is abnormal)	Neutrophils, bands (Stabs) Neutrophils, polymorphonuclear (PMN) Eosinophils Basophils Monocytes Lymphocytes
Coagulation	Activated Partial Thromboplastin Time (aPTT)

	Prothrombin time (INR) Fibrinogen
Enzymes	AST (GOT) ALT (GPT) Alkaline Phosphatase (AP) Creatine Kinase (CK) CK-MB, only if CK is elevated Gamma-Glutamyl Transferase (GGT/ γ -GT) Lactic Dehydrogenase (LDH) Amylase Lipase
Electrolytes	Calcium Sodium Potassium Chloride
Substrates	Glucose BUN (blood urea nitrogen) Uric acid Creatinine ⁶ eGFR (estimated by CKD-EPI formula) (only at screening) Bilirubin Total Bilirubin Direct (if total is elevated) Bilirubin Indirect (if total is elevated) Troponin (Reflex, in case of elevated CK) Protein, Total Albumin C-Reactive Protein (CRP and HS-CRP (high sensitivity – CRP)) ⁵ Cholesterol, total Triglycerides LDL-Cholesterol HDL-Cholesterol
Specific gamma-globulin quantification	IgE ¹
Urine Pregnancy test (only for female patients of childbearing potential)	Human Chorionic Gonadotropin in urine

Serum Pregnancy test (only for female patients of childbearing potential at screening. At later visits only if urine pregnancy test is positive)	
Hormones (only at screening)	TSH (free T3 and free T4 in case of abnormal TSH result)
Urinalysis (dipstick)	Urine Nitrite Urine Protein Urine Glucose Urine Ketone Urobilinogen Urine Bilirubin Urine RBC/ Erythrocytes Urine WBC/ Leukocytes Urine pH
Urine-Sediment (microscopic examination, only if urine analysis abnormal)	Urine Sediment Bacteria Urine Cast in Sediment Urine Squamous Epithelial Cells Urine Sed. Crys., Unspecified Urine Sediment RBC/ Erythrocytes Urine Sediment WBC/ Leucocytes
Urine (only at screening)	Albumin (quantitative)
Infections screening	HBV-DNA (quantitative) at EoT visit ²
Interferon Gamma Release Assay	QuantiFERON®-TB or T-spot at EoT visit ^{3,4}

1 Only in case of allergic reaction

2 HBV-DNA in case of occult HBV infection (for definition see [Table 5.2.3:1](#) footnote 2)

3 Patients with indeterminate QuantiFERON or invalid/borderline T-spot may be retested with IGRA (once) and if inconclusive should have a PPD skin test. .

4 In subjects with a negative QuantiFERON®-TB-Gold Plus or PPD skin test, the test should be repeated at the EoT visit.

5 At screening and at EoT or EOS (as applicable) visits, a blood sample will be obtained to measure hs-CRP. This analysis will be done in the local laboratory.

6 Creatinine can be measured by any of the three serum creatinine assays listed in the table below:

Short name	Name of serum creatinine assay	Substrate	Other information
CREE	Creatinine, enzymatic	creatinine	Enzymatic
CREJIDMS	Creatinine, Jaffe, IDMS	creatinine	Jaffe reaction, IDMS standardized
CREJ	Creatinine, Jaffe, Not IDMS	creatinine	Jaffe reaction, Not IDMS standardized

5.2.4 Electrocardiogram

The 12-lead ECGs must be administered by a qualified technologist and results will be recorded as scheduled in the [Flowchart](#). The investigator or a designee will evaluate whether the ECG is normal or abnormal and assess clinical relevance, if abnormal. ECGs may be repeated for quality reasons and the repeated recording used for analysis.

Additional ECGs may be recorded for safety reasons. Dated and signed printouts of ECG with findings should be documented in patient's medical record.

Clinically relevant abnormal findings will be reported either as baseline condition (if identified at the screening visit) or otherwise as AEs and will be followed up and/or treated as medically appropriate.

Clinically relevant abnormal findings will be reported either as baseline condition (if identified at the screening visit) or otherwise as AEs and will be followed up and/or treated as medically appropriate.

5.2.5 Other safety parameters

All cases of malignancies that are detected during the trial will be reported as SAEs. Patients with a history of malignancy (except for specific cancers) will be excluded from this trial per the exclusion criteria ([Section 3.3.3](#)).

5.2.5.1 Suicidality

Suicidal thoughts and behavior will be assessed by the Columbia-Suicide Severity Rating Scale (C-SSRS, [\[R08-1147\]](#)).

The C-SSRS is a semi-structured, investigator-rated interview, developed by clinical experts in cooperation with the FDA, assessing both suicidal behavior and suicidal ideation. It does not give a global score, but provides some categorical and some severity information specifically for behavior and ideation.

The C-SSRS interview may be administered by any type of physician, psychologist, clinical social worker, mental health counselor, nurse, or coordinator with C-SSRS training. It has a typical duration of five minutes, and causes only a low burden on subjects. At a minimum, the interview consists of 2 screening questions related to suicidal ideation and 4 related to suicidal behavior, and may be expanded to up to 17 items in case of positive responses. Free text entries are allowed for; the investigator has to directly evaluate the scale and write a report. In this trial paper forms will be used for the assessment of the C-SSRS® and results will be transcribed into the e-CRF.

The C-SSRS has been widely used in large multinational clinical trials. The C-SSRS will be administered at the Screening Visit/Visit 1 (using the 'baseline/ screening' version) with the aim to exclude patients with active moderate to severe symptomatology within a specified time prior to the screening or screening visit. The lifetime and the past year history of suicidal ideation and behavior will also be recorded.

After the screening visit, the assessment 'since last visit' version will be performed at each visit. The investigator is to review positive and negative reports for plausibility and clinical relevance. Doubtful reports may be repeated or reports may be validated by a consulting

psychiatrist or other mental health professional expert. If there is a confirmed positive report of suicidal behavior or suicidal ideation type 4 or 5 after start of trial, the investigator is to immediately interview the patient, and/or is to consult a mental health professional. If the positive report is confirmed, appropriate actions for the patient's safety have to be initiated. All C-SSRS reports of suicidal ideation type 4 or 5 and all reports of suicidal behavior must be reported as separate SAEs by the investigator.

For 'Self-injurious behavior, without suicidal intent', standard AE / SAE reporting rules are to be applied.

For each negative report (suicidal ideation type 1, 2 or 3) after the start of the trial, the investigator is to decide based on clinical judgment whether it represents an Adverse Event (AE) as defined in the protocol, and if it is considered an AE then it must be reported accordingly.

5.2.6 Assessment of adverse events

5.2.6.1 Definitions of AEs

5.2.6.1.1 Adverse event

An AE is defined as any untoward medical occurrence in a patient or clinical investigation subject administered a medicinal product and which does not necessarily have to have a causal relationship with this treatment.

An AE can therefore be any unfavourable and unintended sign (including an abnormal laboratory finding), symptom, or disease temporally associated with the use of a medicinal product, whether or not considered related to the medicinal product.

The following should also be recorded as an AE in the CRF and BI SAE form (if applicable):

- Worsening of the underlying disease or of other pre-existing conditions
- Changes in vital signs, ECG, physical examination and laboratory test results, if they are judged clinically relevant by the investigator.

If such abnormalities already exist prior to trial inclusion, they will be considered as baseline conditions and should be collected in the eCRF only.

5.2.6.1.2 Serious adverse event

A serious adverse event (SAE) is defined as any AE, which fulfils at least one of the following criteria:

1. results in death,
2. is life-threatening, which refers to an event in which the patient was at risk of death at the time of the event; it does not refer to an event that hypothetically might have caused death if more severe,
3. requires inpatient hospitalisation or prolongation of existing hospitalisation
4. results in persistent or significant disability or incapacity,
5. is a congenital anomaly / birth defect,

6. is deemed serious for any other reason if it is an important medical event when based on appropriate medical judgement which may jeopardise the patient and may require medical or surgical intervention to prevent one of the other outcomes listed in the above definitions. Examples of such events are intensive treatment in an emergency room or at home for allergic bronchospasm, blood dyscrasias or convulsions that do not result in hospitalisation or development of dependency or abuse.

5.2.6.1.3 AEs considered “Always Serious”

In accordance with the European Medicines Agency initiative on Important Medical Events, Boehringer Ingelheim has set up a list of AEs, which by their nature, can always be considered to be “serious” even though they may not have met the criteria of an SAE as defined above. The latest list of “Always Serious AEs” can be found in the eDC system. A copy of the latest list of “Always Serious AEs” will be provided upon request. These events should always be reported as SAEs as described in [section 5.2.6.2](#).

Cancers of new histology and exacerbations of existing cancer must be classified as a serious event regardless of the time since discontinuation of the drug and must be reported as described in [section 5.2.6.2](#), subsections “AE Collection” and “**AE reporting to sponsor and timelines**”.

5.2.6.1.4 Adverse events of special interest

The term adverse events of special interest (AESI) relates to any specific AE that has been identified at the project level as being of particular concern for prospective safety monitoring and safety assessment within this trial, e.g. the potential for AEs based on knowledge from other compounds in the same class. AESIs need to be reported to the sponsor’s Pharmacovigilance Department within the same timeframe that applies to SAEs, please see [section 5.2.6.2.2](#).

The following are considered as AESIs:

Systemic hypersensitivity including infusion reaction and anaphylactic reaction

Any suspicion of severe infusion reaction systemic / hypersensitivity reaction and of any potential cases of anaphylaxis should be defined and assessed using the criteria discussed in the statement paper from Sampson HA ([Appendix 10.13 \[R11-4890\]](#)).

Severe infections (according to RCTC grading)

Opportunistic and mycobacterium tuberculosis infections

These include pneumocystis jirovecii, BK virus disease including PVAN, CMV, post-transplant lymphoproliferative disorder (EBV), progressive multifocal leucoencephalopathy, bartonellosis (disseminated only), blastomycosis, toxoplasmosis, coccidioidomycosis, histoplasmosis, aspergillosis (invasive only), candidiasis (invasive or pharyngeal), cryptococcosis, other invasive fungi (mucormycosis (zygomycosis, rhizopus, mucor, lichtheimia), scedosporium/pseudallescheria boydii, fusarium), legionellosis, listeria monocytogenes (invasive only), tuberculosis, nocardiosis, non-tuberculous mycobacterium, salmonellosis (invasive only), HBV reactivation, herpes simplex (invasive only), herpes zoster, strongyloides (hyperinfection syndrome and disseminated forms only),

paracoccidioides, penicillium marneffeii, sporothrix schenckii, cryptosporidium species (chronic only), microsporidiosis, leishmaniasis (visceral only), trypanosoma cruzi infection (Chagas' disease) (disseminated only), campylobacteriosis (invasive only), shigellosis (invasive only), vibriosis (invasive due to vibrio vulnificus), HCV progression [[R17-2617](#)].

Hepatic injury

A hepatic injury is defined by the following alterations of hepatic laboratory parameters:

- an elevation of AST (Aspartate Aminotransferase) and/or ALT (Alanine Aminotransferase) ≥ 3 fold ULN combined with an elevation of total bilirubin ≥ 2 fold ULN measured in the same blood draw sample, or in samples drawn within 30 days of each other
OR
- aminotransferase (ALT, and/or AST) elevations ≥ 10 fold ULN.

These lab findings constitute a hepatic injury alert and the patients showing these lab abnormalities need to be followed up according to the "DILI checklist" provided in the ISF. In case of clinical symptoms of hepatic injury (icterus, unexplained encephalopathy, unexplained coagulopathy, right upper quadrant abdominal pain, etc.) without lab results (ALT, AST, total bilirubin) available, the investigator should make sure these parameters are analysed, if necessary in an unscheduled blood test. Should the results meet the criteria of hepatic injury alert, the procedures described in the DILI checklist should be followed.

5.2.6.1.5 Intensity (severity) of AEs

The intensity grading of AEs will be performed according to Rheumatology Common Toxicity Criteria (RCTC) Version 2.0 developed by XXXXXXXXXX [[R13-3515](#)]. Refer to the ISF for intensity/severity classification.

Intensity options are:

- Grade 1 mild
- Grade 2 moderate
- Grade 3 severe
- Grade 4 life-threatening

5.2.6.1.6 Causal relationship of AEs

Medical judgement should be used to determine whether there is a reasonable possibility of a causal relationship between the adverse event and the given study treatment, considering all relevant factors, including pattern of reaction, temporal relationship, de-challenge or re-challenge, confounding factors such as concomitant medication, concomitant diseases and relevant history.

Arguments that may suggest that there is a reasonable possibility of a causal relationship could be:

- The event is consistent with the known pharmacology of the drug.

- The event is known to be caused by or attributed to the drug class.
- A plausible time to onset of the event relative to the time of drug exposure.
- Evidence that the event is reproducible when the drug is re-introduced.
- No medically sound alternative aetiologies that could explain the event (e.g. pre-existing or concomitant diseases, or co-medications).
- The event is typically drug-related and infrequent in the general population not exposed to drugs (e.g. Stevens-Johnson syndrome).
- An indication of dose-response (i.e. greater effect size if the dose is increased, smaller effect size if dose is reduced).

Arguments that may suggest that there is no reasonable possibility of a causal relationship could be:

- No plausible time to onset of the event relative to the time of drug exposure is evident (e.g. pre-treatment cases, diagnosis of cancer or chronic disease within days / weeks of drug administration; an allergic reaction weeks after discontinuation of the drug concerned).
- Continuation of the event despite the withdrawal of the medication, taking into account the pharmacological properties of the compound (e.g. after 5 half-lives).
Of note, this criterion may not be applicable to events whose time course is prolonged despite removing the original trigger.
- Additional arguments amongst those stated before, like alternative explanation (e.g. situations where other drugs or underlying diseases appear to provide a more likely explanation for the observed event than the drug concerned).
- Disappearance of the event even though the trial drug treatment continues or remains unchanged.

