There were no relevant changes compared to placebo for laboratory safety, including clinical chemistry, haematology, coagulation parameters, and urinalysis. No clinically relevant changes were observed in 12-lead ECGs, vital signs, and cardio-monitoring.

PK analysis showed that exposure (AUC_{0-tz} and C_{max}) to spesolimab increased with increasing dose in an approximately dose-proportional manner from 0.3 to 10 mg/kg.

The effective half-life of spesolimab is approximately 4 weeks in the linear dose range. Overall, PK data so far suggests target-mediated drug disposition (TMDD) kinetics for

spesolimab. Anti-drug antibodies (ADA) were detected in 8 patients, 3 of those had pre-existing levels. Pharmacodynamic effects in this FIH Single Rising Dose trial [[c03361085](#)] were assessed by indirect target engagement (ITE) of IL36R by spesolimab using an ex-vivo whole blood stimulation assay. Preliminary analyses indicate that $\geq 94\%$ peripheral IL36R receptor occupancy is achieved with doses $\geq 0.05\text{mg/kg}$ from 30 minutes post infusion to 10 weeks.

In a multiple rising dose trial, spesolimab or placebo have been administered to healthy volunteers at multiple ascending i.v. doses of 3, 6, 10 and 20 mg/kg given qw for 4 weeks (i.e. 4 administrations) or a single dose of 20mg/kg (8 subjects each, 3:1 on active or PBO). Overall, spesolimab was well tolerated. There were no dose dependent AEs, AEs considered to be dose limiting and no SAEs. In all cases the AEs were of mild or moderate intensity. Furthermore, there were no clinically relevant abnormalities on treatment with spesolimab with respect to safety laboratory, vital signs, or ECGs as assessed by a central reader. For further details and most recent results refer to the current Investigator's Brochure (IB) [[c03320877-09](#)].

Studies in Patients

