Efficacy data are available from a proof of concept study in patients with generalized pustular psoriasis (GPP). In trial 1368.11, seven patients received a single intravenous dose of 10 mg/kg spesolimab, and were monitored for 20 weeks. At week 1 after dosing, Generalized Pustular Psoriasis Physician Global Assessment (GPPGA) score of clear or almost clear (0 or 1) was achieved in five patients, and by Week 4 in all seven patients. Within 48 hours post dose, pustules were completely cleared in three patients, by week 1 in five patients and by week 2 in six of seven patients. A major improvement in (GPPASI) was observed in all patients with a mean (SD) percent change from baseline of 73.2% (16.2) at week 2; by week 4, this was further reduced to 82.0% and was maintained to week 20 (83.6%).

Residual Effect Period

The Residual Effect Period (REP) of spesolimab is 16 weeks. This is the period after the last dose with measurable drug levels and pharmacodynamic effects still likely to be present.

Summary

Spesolimab is an anti IL36R antibody with a high clinical activity to block IL36R signaling, as demonstrated in patients with Generalized Pustular Psoriasis, a severe inflammatory skin disease driven by uncontrolled IL36 activity. Spesolimab has been tested in healthy volunteers with multiple dosing up to four weeks of 20 mg/kg i.v. q.w. which were all safe and well tolerated. In addition, IL36R inhibition shows a favourable nonclinical safety profile. Therefore, spesolimab might be a promising drug to treat patients suffering from hidradenitis suppurativa.

For further details and most recent results refer to the current IB [[c03320877-09](#)].

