1.4.2 Risks

[Table 1.4.2:1](#) lists possible risks for spesolimab as well as theoretical risks derived from general safety considerations of immunomodulatory drugs and from this trial specific procedures.

No other IL-36 receptor antagonist is currently approved, providing information on identified risks in molecules of this class.

In order to protect the patient's safety during conduct of this trial, an independent Data Monitoring Committee (DMC) has been established for the periodic review of clinical trial safety data.

Table 1.4.2:1 Overview over trial related risks

Hypothetical risks of clinical relevance for this trial	Summary of data, rationale for the risk	Mitigation strategy
Spesolimab		
Drug-induced liver injury (DILI)	Although rare, a potential for drug-induced liver injury (DILI) is under constant surveillance by sponsors and regulators. Therefore, DILI is considered as a standard risk in all BI development programs.	Timely detection, evaluation, and follow-up of laboratory alterations in selected liver laboratory parameters to ensure patients' safety. See also section 5.2.6 , adverse events of special interest. Trial treatment discontinuation criteria as well as criteria for trial treatment restart are implemented for relevant cases.
Systemic Hypersensitivity reaction	After administration of any biologic agent or protein, there is a possibility of occurrence of immediate (such as anaphylaxis) or delayed (such as drug reaction with eosinophilia and systemic symptoms) adverse immune reactions	Patients with a history of allergy/hypersensitivity to the systemically administered trial medication agent or its excipients are excluded from the trial. In case of systemic hypersensitivity reactions including anaphylactic reaction emerging during or after administration of trial medication, the investigator should consider in accordance with the severity of the reaction and local standard of care to interrupt and treat the condition. Systemic hypersensitivity reaction is defined as an adverse event of special interest (AESI). It is subject to close monitoring

		and investigators are requested to assess these conditions using the criteria discussed in the statement paper from Sampson HA [R11-4890].

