5.2.6.2 Adverse event collection and reporting

5.2.6.2.1 AE Collection

The investigator shall maintain and keep detailed records of all AEs in the patient files. For patients not rolling over to OLE trial, the following must be collected and documented on the appropriate CRF(s) by the investigator:

- From signing the informed consent onwards until the individual patient's end of study:
all AEs (serious and non-serious) and all AESIs.
- After the individual patient's end of study:
the investigator does not need to actively monitor the patient for new AEs but should only report any occurrence of cancer and trial treatment related SAEs and trial treatment related AESIs of which the investigator may become aware of by any means of communication, e.g. phone call. Those AEs should be reported on the BI SAE form (see [section 5.2.6.2.2](#)), but not on the CRF.

For patients rolling over to OLE trial the following must be collected and documented on the appropriate CRF(s) by the investigator:

- From signing the informed consent of the parent trial onwards until the first dose of trial medication in the extension trial:
all AEs (serious and non-serious) and all AESIs.

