The frequency of patients with AEs will be summarised by treatment, primary system organ class and preferred term. AEs which were considered by the investigator to be drug related will be summarised separately. Separate tables will also be provided for patients with SAEs, patients with AESIs, patients with AE leading to discontinuation of the trial medication, and patients with other significant AEs (as described previously). AEs will also be summarized by maximum intensity.

For disclosure of AE data on ClinicalTrials.gov, the frequency of patients with non-serious AEs occurring with an incidence of greater than 5 % (in preferred terms) will be summarised by treatment, primary system organ class and preferred term. The frequency of patients with SAEs and drug related SAEs will also be summarised respectively.

For disclosure of AE data in the EudraCT register, the frequency of non-serious AEs with an incidence of greater than 5 % (in preferred terms) and the frequency of SAEs will be summarised.

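### The causality guidance gives an allergic reaction some weeks after stopping as an example of implausible onset, which does not fit this antibody's half-life and 16-week residual effect period

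*Protocol*

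**What the plan says.** Protocol 5.2.6.1.6 asks the investigator to use medical judgement and weigh all relevant factors, and then offers two lists of considerations. The second list opens with "Arguments that may suggest that there is no reasonable possibility of a causal relationship could be". Its first item is the lack of a plausible onset time relative to exposure, and one of the illustrations is "an allergic reaction weeks after discontinuation of the drug concerned". That item does not mention half-life or residual effect. The next item, on events that continue after withdrawal, does: they are to be judged "taking into account the pharmacological properties of the compound (e.g. after 5 half-lives").

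Other sections describe how long this drug persists and what it may cause:

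- Protocol 1.2.1: "The effective half-life of spesolimab is approximately 4 weeks in the linear dose range".
- Protocol 1.2.1, on the 16-week residual effect period (REP): "This is the period after the last dose with measurable drug levels and pharmacodynamic effects still likely to be present".
- Protocol 1.4.2, risk table: possible immune reactions are either immediate or "delayed (such as drug reaction with eosinophilia and systemic symptoms) adverse immune reactions".
- Protocol 7.2.5: adverse events from the start of treatment to the end of the REP count as treatment-emergent.

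The investigator's judgement is then used in the analysis. SAP 7.8.1 states: "AEs which were considered by the investigator to be drug related will be summarised separately". The same section plans a summary of drug-related SAEs for registry disclosure.

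**The concern.** The example would suit a drug that is cleared within days. For an antibody with a half-life of about 4 weeks, the weeks after stopping are still weeks of exposure. An investigator who follows the example would count late onset against causation in a period when the protocol itself expects drug and effect to be present.

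The event type matters too. Systemic hypersensitivity is an adverse event of special interest (Protocol 5.2.6.1.4), and SAP Table 7.8.1: 1 sets up searches for hypersensitivity and for drug reaction with eosinophilia and systemic symptoms. The plan looks for such reactions, while its causality guidance uses late allergic onset as an illustration of non-causation. What is at stake is the attribution of late hypersensitivity in the drug-related summaries, not whether the events are recorded.

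**Working it through.** The plan states no figure to reproduce. The check has two parts: how much drug remains in the period that the example describes, and which outputs depend on the causality call.

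**1. Drug remaining after the last dose**

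Inputs: half-life about 4 weeks and REP 16 weeks (both Protocol 1.2.1). Half-lives of 3 and 5 weeks are added as an assumed range. Discontinuation is counted from the last dose.

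Formula: share remaining = 0.5^(weeks ÷ half-life).

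| Weeks after last dose | 3-week half-life (assumed) | 4-week half-life (protocol) | 5-week half-life (assumed) |
|---|---|---|---|
| 1 | 79% | 84% | 87% |
| 2 | 63% | 71% | 76% |
| 4 | 40% | 50% | 57% |
| 8 | 16% | 25% | 33% |
| 16 | 2.5% | 6% | 11% |

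Example at 4 weeks: 0.5^(4 ÷ 4) = 0.50. At 8 weeks: 0.5^(8 ÷ 4) = 0.25.

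The REP is 16 ÷ 4 = 4 half-lives, and 16 × 7 = 112 days. This matches the end-of-study visit in the flowchart and the on-treatment definition in SAP Table 6.1: 1. The plan's safety window thus already follows the drug's persistence; the onset example does not.

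**2. What depends on the causality call**

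- Does not depend on it: collection of all AEs and AESIs to end of study (Protocol 5.2.6.2.1), reporting of AESIs within 24 hours (5.2.6.2.2), treatment-emergent AE tables (7.2.5), and the AESI table and hypersensitivity searches (SAP 7.8.1).
- Depends on it: the summaries of drug-related AEs and drug-related SAEs (SAP 7.8.1).
- Depends on it after end of study only: at that point the investigator "should only report any occurrence of cancer and trial treatment related SAEs and trial treatment related AESIs". For patients not entering the extension, end of study is scheduled 16 weeks after the last dose, when the REP is over (Protocol 6.1). Within the REP this restriction matters only for patients whose participation ends early.

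**3. Who is exposed to the problem**

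The patients concerned are mainly those who stop early or do not enter the extension. Patients who roll over do so at Week 12, two weeks after their Week 10 dose, and are then followed in the extension.

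**The case against.** The strongest defence is that the guidance does not dictate the answer. It puts medical judgement first, and both the list heading and the example are permissive. The governing criterion is onset relative to exposure, so an investigator who knows the REP can treat those weeks as exposure. The opposing list offers arguments for relatedness, including plausible onset and event types that are typically drug-related. All of this stands, and it limits the effect to a nudge. It does not remove the mismatch, because the example names the event type in question and carries no qualifier.

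It can also be said that no section states outright that an allergic reaction first appearing weeks after stopping is plausible. The delayed reactions in the risk table are timed from administration, and the work-up in 4.2.1.1 does not address onset after stopping. This is fair: the conflict is inferred from the half-life, the REP and the treatment-emergent window. Those three are enough to show that timing alone does not make such a reaction implausible.

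A reader might infer more, and the documents do not support it:

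- *That 5.2.6.1.6 contradicts itself.* The 5-half-lives remark concerns continuation of an event, not its onset. These are different criteria.
- *That SUSAR identification is affected.* Protocol 4.1.5.2 mentions SUSARs only in connection with access to the randomization code. No section says how the investigator's call determines SUSAR status.
- *That late reactions would generally go unreported after end of study.* For patients followed as scheduled, the restriction to related events begins only when the REP ends.

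**Conclusion.** The point holds in a limited form. The onset example does not fit the protocol's own half-life, residual effect period and treatment-emergent window, or its listing of delayed immune reactions as a risk. With about half the drug still present at 4 weeks and a quarter at 8, onset in that period cannot be dismissed on timing. The consequence is a bias towards 'not related' for late hypersensitivity within the REP, confined to the drug-related AE and SAE summaries. Event capture, treatment-emergent counts and AESI counts are unaffected.

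The number of events affected is unknown, and no effect on any trial conclusion is shown.

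The decay figures assume simple first-order elimination and ignore absorption after subcutaneous dosing. The protocol notes target-mediated kinetics, so elimination may differ at low concentrations. The conclusion for the first weeks does not rest on that tail: with half-lives of 3 to 5 weeks, 40% to 57% remains at 4 weeks.

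**What to change.** In Protocol 5.2.6.1.6, delete the allergic-reaction example. Alternatively, reconcile it with sections 1.2.1 and 7.2.5 by stating that time to onset is judged against the compound's half-life and 16-week REP, as the next item already does in principle for continuing events. Deletion is simpler and leaves no residual wording to interpret.

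The cost is one line of protocol or investigator guidance, with no change to visits, data collection, sample size or planned tables. The downside is that a few more late reactions may be classed as drug-related, some of which may have another cause.
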